15.1.2. MISSING DATA METHODS FOR PRIMARY EFFICACY VARIABLE

Subjects with missing primary efficacy values will be imputed as non-responders for clinical remission and response at Week 8. Missing MMS scores at Week 8 will be imputed as mentioned in section 7.3.

15.1.3. PRIMARY ANALYSIS OF PRIMARY EFFICACY VARIABLE

The primary efficacy analysis will be performed for FAS and PPAS.

The primary objective of this study is to determine an optimal ABX464 dose to be used in moderate to severe active ulcerative colitis patients who have failed or are intolerant to immunomodulators, Anti-TNF α , vedolizumab, JAK inhibitors and/or corticosteroids by comparing the mean change from baseline in the MMS at Week 8 for the three ABX464 dose levels to the placebo. An analysis of covariance (ANCOVA) model will be used to assess these changes.

The ANCOVA model for Change from Baseline MMS at Week 8 will include the fixed treatment effect, the previous use of biological or JAK inhibitors effect and the covariate, baseline MMS and a random error term.

The assumptions that the random errors in the ANCOVA model are normally distributed with homogeneity of variances will be checked. If either the hypothesis regarding normality of errors or the hypothesis of equal variances is rejected at the 5% significance level a nonparametric ANCOVA using the ranked data will be performed to test for differences in the mean change from baseline. The least square means and confidence intervals from the parametric ANCOVA will also be presented.

The dose testing will commence with comparing the ABX464 50mg dose with placebo. If this is significant at a 5% two-sided level (i.e. $p < 0.05$) a comparison against placebo will be carried out at the ABX464 100mg dose. Again, if significance at a 5% level for this test is observed the procedure will be repeated at the ABX464 25mg dose. If in this sequence of comparisons of ABX464 dose levels to placebo one is not significant (i.e., $p \geq 0.05$) the additional comparisons to placebo will not be

Document: \\iedc-vnasc01\BIOSdata\Abivax\ABX464\FZA92720\Biostatistics\Documentation\SAP\ABX464-103_SAP_V2.0_10MAY2021

Author: [REDACTED]

Version Number:
Version Date:

2.0
10May2021

Template No.: CS_TP_BS016 Revision 5

Reference: CS_WI_BS005

Effective Date: 01Apr2018

performed. Should any of these comparisons with the placebo treatment group be significant, further exploratory testing of the dose groups against each other will be conducted at the same significance level. A global comparison of all active treatment groups vs placebo group will also be conducted.

Descriptive statistics for MMS and change from baseline MMS at every visit assessed will be summarized by treatment arm in a table and displayed graphically. A by subject listing of the MMS values and change from baseline value will also be presented.

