9.2. Efficacy Analysis

Analysis of efficacy data will be carried out in the Full Analysis Set in which subjects who prematurely discontinue the study due to adverse reaction(s) will be considered treatment failures.

The primary efficacy endpoint of the study is the change in the Modified Mayo Score (MMS) from Baseline to Week 8. This change will be compared between subjects who received ABX464 and placebo for each ABX464 treatment arm separately using an ANCOVA model adjusting for randomized study treatment arm, previous biological or JAK inhibitors treatment use (i.e. randomization strata), and baseline MMS.

The dose testing will commence with comparing the ABX464 50mg dose with placebo. If this is significant at a 5% two-sided level (i.e. $p < 0.05$) a comparison against placebo will be carried out at the ABX464 100mg dose. Again, if significance at a 5% level for this test is observed the procedure will be repeated at the ABX464 25mg dose. In this closed procedure no adjustment for multiple comparison is needed. Should the data warrant it, testing between doses may also be conducted.

In addition, descriptive statistics will be presented by treatment arm for all secondary efficacy variables for each measurement timepoint.

These statistics include:

- Continuous variables: mean, standard deviation, minimum and maximum, 95%
- Confidence intervals for the mean, median and quartiles will be presented.
- Categorical variables: counts, rates and 95% confidence intervals for the rates will be calculated.

In addition to descriptive statistics, the following analyses will also be carried out for the variables indicated below:

- The global (combined) ABX464 treatment effect vs. placebo in the change from Baseline in Modified Mayo Score at Week 8
- The proportion of subjects with clinical remission at Week 8 will be compared across study treatment arms using a stratified Mantel-Haenszel test.
- Mixed model analysis of covariance will be conducted for the following measurements:
 - The change from baseline in microRNA-124 levels in total blood (PAXgene®) at Week 1, Week 4, Week 8 and Week 16 and in tissue (RNA later).
 - The change from baseline in fecal calprotectin levels at Week 8 and Week 16.
 - The change from screening in the histopathology/infiltrate (rectal/sigmoidal biopsies) assessed by the Robarts Histopathology Index, the Geboes and Nancy Histology Scoring Scales at Week 8 and Week 16 (if available).

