2.3. ESTIMANDS

The primary and secondary estimands to support regulatory decisions are described in Table A below. The intercurrent event is the early discontinuation of patients from the study and/or missing Week 8 efficacy assessments.

Table A List of Estimands

Document: \\ieddc-vnasc01\BIOSdata\Abivax\ABX464\FZA92720\Biostatistics\Documentation\SAP\ABX464-103_SAP_V2.0_10MAY2021

Author: [REDACTED]

Version Number: 2.0
Version Date: 10May2021

Template No.: CS_TP_BS016 Revision 5

Reference: CS_WI_BS005

Effective Date: 01Apr2018

Estimand	Definition	Attributes			
		Population	Variable/Endpoint	Intercurrent event handling strategy	Population-level summary measure
Primary	Optimal ABX464 dose	All patients randomized, received at least one dose of study drug and provided at least one efficacy data point	Mean change in MMS from baseline to Week 8	Missing Week 8 MMS components (stool frequency, rectal bleeding and endoscopy subscores) will be imputed using methods detailed in section 7.3.	Mean change from baseline
Secondary	The effect of different dose groups vs placebo on secondary variables	All patients randomized, received at least one dose of study drug and provided at least one efficacy data point	Mean change from baseline to Weeks 8 and 16 in pMMS	Missing Week 8 pMMS components (stool frequency and rectal bleeding subscores) will be imputed using methods detailed in section 7.3.	Mean change from baseline
			Clinical remission or response at Weeks 8 and 16	Patients with missing Week 8 assessment will be considered non-responders	Proportion of responders in each treatment group
			Mean change from baseline to Week 8 in fecal calprotectin and CRP levels	Missing fecal calprotectin and CRP values will not be imputed.	Mean change from baseline

Document: \\ieddc-vnasc01\BIOSdata\Abivax\ABX464\FZA92720\Biostatistics\Documentation\SAP\ABX464-103_SAP_V2.0_10MAY2021

Author: [REDACTED]

Version Number: 2.0
 Version Date: 10May2021

Template No.: CS_TP_BS016 Revision 5

Reference: CS_WI_BS005

Effective Date: 01Apr2018

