15. EFFICACY OUTCOMES

15.1. PRIMARY EFFICACY

15.1.1. PRIMARY EFFICACY VARIABLE & DERIVATION

The primary efficacy variable is the reduction from baseline in MMS at Week 8 (Day 57).

The MMS will be obtained from the MMS eCRF page with raw.MMS.MMSSCR and confirmed by eDiary entries. The MMS ranges from 0 to 9 and is derived from the sum of 3 sub-scores ranging from 0 to 3 for stool frequency, rectal bleeding and mucosal appearance at endoscopy respectively, with a lower score indicating less severe or no ulcerative colitis (UC) (See APPENDIX 2). The MMS determined at screening will be used as baseline MMS, as MMS is not calculated at Day 1.

Change from baseline is described in Section 6.6.

Document: \\ieedc-vnasc01\BIOSdata\Abivax\ABX464\FZA92720\Biostatistics\Documentation\SAP\ABX464-103_SAP_V2.0_10MAY2021

Author: [REDACTED]

Version Number: 2.0
Version Date: 10May2021

Template No.: CS_TP_BS016 Revision 5

Reference: CS_WI_BS005

Effective Date: 01Apr2018

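### A pre-test can replace the primary ANCOVA with a rank ANCOVA that does not test the mean change; the realistic cost is lost power if only a subset responds

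*SAP*

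**What the plan says.** The target is a mean. The estimand table in SAP 2.3 gives the primary variable as "Mean change in MMS from baseline to Week 8". SAP 15.1.3 states the objective as "comparing the mean change from baseline in the MMS at Week 8 for the three ABX464 dose levels to the placebo" and continues: "An analysis of covariance (ANCOVA) model will be used to assess these changes". Protocol 9.2 likewise compares each dose with placebo "separately using an ANCOVA model adjusting for randomized study treatment arm" and has no fallback; neither has the Synopsis.

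SAP 15.1.3 then adds a conditional step. Its trigger reads: "If either the hypothesis regarding normality of errors or the hypothesis of equal variances is rejected at the 5% significance level". The consequence, once either check fails, is that "a nonparametric ANCOVA using the ranked data will be performed to test for differences in the mean change from baseline". From the parametric model it keeps this: "The least square means and confidence intervals from the parametric ANCOVA will also be presented". It does not mention a parametric p-value for that case.

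The next paragraph starts the fixed sequence (50 mg, then 100 mg, then 25 mg, each at p<0.05) without saying which model supplies the p-value. The SAP names neither the normality test nor the variance test, and it does not say whether baseline is ranked along with the response. SAP 3.3, which lists changes from the protocol, does not mention the switch.

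**The concern.** A rank ANCOVA tests a shift in mean rank. That amounts to a test of means only if the treatment moves the whole distribution by a constant. One of the two triggers, unequal variance, is itself evidence against a constant shift. So the sentence promises something the method does not deliver, in the circumstances where the difference matters most.

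The gating p-value and the reported effect could then part company. The LS mean difference could have a CI that excludes zero while the rank test at 50 mg is not significant. The sequence would stop and 100 mg and 25 mg would go untested. The primary test would also be settled only after looking at the outcome data, by pre-tests that the SAP does not name.

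**Working it through.** **1. The plan's own figure.** Protocol 9.4 assumes mean reductions of 2.5 and 1.0 (difference 1.5), SD 2.1, two-sided 5%, a two-sample t-test, gated testing, power above 90% and 5% dropout.

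- With 55 evaluable per arm, the noncentrality is 1.5 / (2.1 × √(2/55)) = 3.75, which gives 96.0% power per comparison.
- The probability of passing all three gated t-tests against one placebo arm (1,000,000 simulated trials) is 89.7% at 54 per arm and 90.3% at 55.
- 55 / 0.95 = 57.9, so 58 per arm, and 4 × 58 = 232.

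This is the stated figure before the pandemic increase to 244. The trial was sized for a parametric test of means.

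**2. How often the switch fires.** If errors are exactly normal with equal variance, two independent 5% tests fire in 1 − 0.95² = 9.75% of trials. The real endpoint is coarser: "The MMS ranges from 0 to 9 and is derived from the sum of 3 sub-scores". Rounding and bounding alone make the normality test reject often.

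**3. Simulation of 50 mg against placebo.** The assumptions, none of them from the SAP, are:

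- Shapiro-Wilk and Levene tests on the ANCOVA residuals; response and baseline both ranked.
- Four arms of 58; half with prior biologic or JAK exposure; baseline MMS 5 to 9 with probabilities 15, 20, 30, 25 and 10%.
- 4,000 trials per setting in settings A, B, C and E.

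| Setting | Switch fires | ANCOVA rejects | Planned rule rejects | ANCOVA and rank test disagree |
|---|---|---|---|---|
| A. Normal errors, no effect | 9% | 4.2% | 4.3% | 1.8% |
| A. Normal errors, 1.0 vs 2.5 | 9% | 96.6% | 96.5% | 1.6% |
| B. Rounded and bounded 0-9, no effect | 65% | 5.4% | 5.4% | 2.0% |
| B. Rounded and bounded 0-9, 1.0 vs 2.5 | 28% | 95.7% | 95.5% | 1.1% |
| C. Mixture, 15% large responders in every arm | 100% | 5.4% | 5.1% | 3.9% |
| C. Mixture, 15% vs 45% large responders | 100% | 89.7% | 83.9% | 6.2% |
| D. 25-30% large responders on active, the rest like placebo | 100% | 81-92% | 66-81% | 11-16% |
| E. Equal means, different shapes | 100% | 2-3% | 24-56% | 24-56% |

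In C, the reduction is 5 for large responders and 0.3 otherwise, with SD 1.0, rounded and bounded. In D, the size and spread of the large response are likewise assumed. With 55 per arm, the switch fired in 64% of trials under no effect and 23% at a difference of 1.5, and the planned rule rejected in 4% and 95%.

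**4. A second look at the subset case.** With 55 per arm, 15-35% of active patients improving by 4 to 5 points and the rest like placebo, the planned rule against ANCOVA gave, for example, 55% vs 59%, 59% vs 71% and 89% vs 94%. It rejected in favour of placebo in 0-0.1% of trials.

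**5. Why power falls.** The mean counts how far a large responder moves. The rank counts only how many other patients are passed. When a minority moves a long way, ranking discards much of the signal.

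**6. What setting E requires.** In one version, 25% of active patients improve by 4 and the rest by 0, so the active mean is 0.25 × 4 + 0.75 × 0 = 1.0, equal to placebo. The other 75% then do 1.0 point worse than placebo. In general, if placebo improves by 1.0 and 30% of active patients improve by 5, equal means require the other 70% to change by (1.0 − 0.30 × 5) / 0.70 = −0.71, that is, to worsen.

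**The case against.** The strongest reply is that the fallback is pre-specified and rule-based, in a phase IIb dose-ranging trial, on a bounded ordinal composite for which rank analysis is defensible. The parametric LS means and CIs are always presented, so the estimand is still estimated. All of this is true. It does not rescue the claim that the rank test assesses mean change, nor does it say which p-value gates.

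Three stronger readings are tempting, and none is supported.

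- **Inflated type I error, or findings in favour of placebo.** A reader might infer this from setting E. When the whole distributions are equal, the planned rule rejects in about 4-5% of trials. Setting E needs most treated patients to do worse than placebo. Nothing in the documents suggests that: Protocol 1.3 reports clinical response of 70% on active against 33% on placebo in the phase IIa study.
- **Unequal variance alone breaks the rule.** With equal means and symmetric errors (SD 1.5 vs 2.5, 1.2 vs 2.8, 2.1 vs 2.8), the planned rule rejected in 3.6-3.9% of trials and ANCOVA in 3.1-3.7%. The divergence comes from differing shapes.
- **The SAP says the rank p-value drives the gate.** It does not. That is the natural reading, because the rank procedure is the one named as the test, but it remains an inference.

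The size of the effect also depends on assumed shapes. The simulated baselines leave out patients with MMS 4 enrolled under the original protocol (SAP 5.2.4). Because missing Week 8 scores are imputed, the FAS model could have up to 244 residuals rather than the 232 simulated.

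**Conclusion.** The point holds in a limited form. The mismatch between a rank test and a mean-change estimand follows from the text and needs no simulation. So do the undefined gating p-value and the unlisted departure from the protocol.

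The switch would probably be used: about 60% of trials under no effect, 23-28% at the design difference and about 100% with bimodal responses. Where the treatment acts as a shift, this hardly matters: the tests disagree in 1-2% of trials, and power is about 95-96% either way. The realistic harm is lost power when only a subset responds, about 66-81% against 81-92%, with the tests disagreeing in 11-16% of trials. Through the sequence, a failure at 50 mg also removes the 100 mg and 25 mg tests.

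These figures rest on assumed pre-tests, ranking method and response shapes. They indicate direction and rough size; they do not predict this trial. The paragraph should be changed, but the rule does not invalidate the design.

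**What to change.** Rewrite the paragraph in SAP 15.1.3, before unblinding, so that:

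- the parametric ANCOVA is the only test that feeds the dose sequence, with no normality or variance pre-test;
- its p-value and CI both use heteroscedasticity-robust (HC3) standard errors, which deal with unequal variances without a switch;
- rank ANCOVA is reported as a sensitivity analysis, stating what is ranked and describing it as a comparison of mean ranks;
- residual plots are descriptive only.

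The robust standard errors should be listed in SAP 3.3. If the sponsor prefers to keep the switch, the SAP must at least name both pre-tests, say which p-value gates, stop calling the rank procedure a test of means, and list the switch in SAP 3.3.

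The cost is one SAP paragraph. The sample size stays at 244, and power at the assumed shift of 1.5 is unchanged at about 95-96%. The p-value, estimate and CI then address the same estimand.

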15.1.4. SENSITIVITY ANALYSIS OF PRIMARY EFFICACY VARIABLE

15.1.4.1. Per Protocol Analyses

The primary efficacy analysis will be repeated for the PPAS. Similar output will be displayed for these results.

15.1.4.2. Subgroup Analyses

The primary efficacy analysis will be repeated for the subgroups Age, Gender, concomitant UC medications, with/without previous biological or JAK inhibitors exposure and Baseline MMS, as explained in Section 7.5.

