9.4. Determination of Sample Size

The primary endpoint is the change in the Modified Mayo Score (MMS) from Baseline to Week 8. The primary endpoint will be compared between subjects who received ABX464 and placebo for each ABX464 treatment arm separately.

For the sample size calculation, the following assumptions were made:

- mean reduction in MMS (ABX464): 2.5
- mean reduction in MMS (placebo): 1.0
- pooled standard deviation of reduction in MMS: 2.1
- Type 1 error: 5% two-sided.
- Treatment testing to use a sequential, gate-keeping strategy, where treatment arms will be tested in the following order: ABX464 50mg vs. placebo, ABX464 100mg vs. placebo, ABX464 25mg vs. placebo. Subsequent tests will only be performed only if prior test(s) are significant ($p<0.05$).
- >90% power
- Two-sample t-test
- 5% dropout rate prior to Week 8 MMS assessment (all treatment arms)
- 1:1:1:1 (ABX464 100mg: ABX464 50mg: ABX464 25mg: placebo) study treatment arm allocation ratio.

If the above assumptions hold true, then a total sample size of 232 subjects will be required to be randomized (58 subjects randomized to each study treatment arm).

Due to the SARS Cov-2 pandemic the drop-out rate of the study is expected to be somewhat higher than originally estimated. Therefore, an additional 12 subjects are planned to be recruited in the study leading to an overall sample size of 244 patients (61 subjects randomized to each study treatment arm).

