3.3. CHANGES TO ANALYSIS FROM PROTOCOL

The FAS population will include subjects who received at least one dose of study treatment, and who have baseline data for at least one efficacy variable.

Descriptive statistics for electrocardiogram (ECG) parameters will not be calculated as per protocol.

Individual parameter results will be kept on site, but only the number of patients with normal, abnormal - not clinically significant (NCS) and abnormal - clinically significant (CS) results will be reported.

Potentially Clinically Significant Abnormalities (PCSA) will not be considered due to data unavailability.

The Country and US vs Non-US subgroup analyses will not be performed because of the small number of subjects from some countries.

Analyses of miRNA-124 levels in blood and tissue will be analysed and reported separately by an independent vendor and will be excluded from the final outputs and analysis conducted by IQVIA.

Additionally, pharmacokinetic (PK) results will also be reported separately by an independent vendor, but external data may be made available to IQVIA Biostatistics and the subgroup 'Week 16 ABX464-NGlu AUC0-12 level above/below 7 000 h*ng/mL' will be included in subgroup analyses, if available.

The analysis of the following secondary endpoints will not be addressed in this SAP:

- Change relative to baseline in miRNA-124 expression
- Change relative to baseline in infiltrate/histopathology (Sigmoidal) using the RHI
- IL-6, TNF α , IL-1b, IL-10 plasma concentrations
- Serum concentration of ABX464 and N-Glucuronide ABX464

Document: \\ieedc-vnasc01\BIOSdata\Abivax\ABX464\FZA92720\Biostatistics\Documentation\SAP\ABX464-103_SAP_V2.0_10MAY2021

Author: [REDACTED]

Version Number:
Version Date:

2.0
10May2021

Template No.: CS_TP_BS016 Revision 5

Reference: CS_WI_BS005

Effective Date: 01Apr2018

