7.5. EXAMINATION OF SUBGROUPS

Subgroup analyses will be conducted as described in relevant efficacy analysis sections. It should be noted that the study was not designed to detect treatment differences with high statistical power within subgroups.

Analyses will be performed for the following subgroups:

- Gender:

Female

Male

- Age (years):

<30

≥30 to <65

≥65

- Country/Region

Austria	Netherlands
---------	-------------

Belarus	Poland
---------	--------

Belgium	Serbia
---------	--------

Canada	Slovakia
--------	----------

Czech Republic	Slovenia
----------------	----------

France	Spain
--------	-------

Germany	Ukraine
---------	---------

Hungary	United Kingdom
---------	----------------

Italy	US
-------	----

North America (US and Canada).

Western Europe: Italy, France, Germany, Netherlands, Austria, Belgium, Spain, United Kingdom

Eastern Europe: Slovakia, Slovenia, Ukraine, Poland, Czech Republic, Serbia, Hungary, Belarus

- Baseline MMS:

Document: \\ieedc-vnasc01\BIOSdata\Abivax\ABX464\FZA92720\Biostatistics\Documentation\SAP\ABX464-103_SAP_V2.0_10MAY2021

Author: [REDACTED]

Version Number: 2.0
Version Date: 10May2021

Template No.: CS_TP_BS016 Revision 5

Reference: CS_WI_BS005

Effective Date: 01Apr2018

4
5 to 6
7 to 9

- With/without previous biological or JAK inhibitors exposure
- Concomitant UC medications
 - Corticosteroids
 - Immunosuppressants
 - 5ASA

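### Subgroup effects are judged by repeating the primary analysis inside each level, with no treatment-by-subgroup interaction, so chance differences in significance can look like differences in effect

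*SAP*

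**What the plan says.** SAP 15.1.4.2, under the sensitivity analyses of the primary variable, reads: "The primary efficacy analysis will be repeated for the subgroups Age, Gender, concomitant UC medications". It then adds prior biologic/JAK exposure and baseline MMS, and refers to SAP 7.5 for the levels.

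The analysis to be repeated is set out in SAP 15.1.3. It is an ANCOVA of the Week 8 change in MMS on treatment, prior biologic/JAK use and baseline MMS. Testing starts with 50 mg versus placebo, moves to 100 mg and then to 25 mg, each at 5% two-sided. Once a test fails, later comparisons with placebo are not made. SAP 15.1.4.2 takes nothing out of this for subgroups.

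SAP 7.5 gives the levels: two for gender, three for age, three for baseline MMS (4, 5 to 6, 7 to 9), with or without prior exposure, and three concomitant UC medication classes. It cautions that "the study was not designed to detect treatment differences with high statistical power within subgroups". The only interaction in either document is visit by treatment, in the repeated-measures model of SAP 15.2.3.3.

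On geography, SAP 3.3 says: "The Country and US vs Non-US subgroup analyses will not be performed". SAP 7.5 still lists 18 countries and three regions.

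**The concern.** A subgroup analysis asks whether the treatment effect differs between levels. That is a question about the difference between two effects. A p-value in men and another in women do not answer it: with smaller numbers, and often unequal ones, one can fall below 5% and the other above it when the true effect is the same in both.

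Two things are at stake. First, the planned output gives a reader nothing with which to tell a chance pattern from a real one. Second, the gate was built for the primary family of tests. Carried into each level, it withholds the 100 mg and 25 mg comparisons with placebo wherever 50 mg misses 5%. In a trial whose primary objective is to choose a dose, consistency of all three doses across patient types is what the subgroup tables should show.

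**Working it through.** **Inputs from Protocol 9.4.** "Type 1 error: 5% two-sided"; "mean reduction in MMS (ABX464): 2.5"; "mean reduction in MMS (placebo): 1.0"; "pooled standard deviation of reduction in MMS: 2.1"; 5% dropout; 58 randomised per arm, raised to 61. The difference is 2.5 − 1.0 = 1.5.

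**The plan's own figure.** 58 × 0.95 ≈ 55 evaluable per arm. SE = 2.1 × √(2/55) = 0.400, so the noncentrality is 1.5/0.400 = 3.75. Two-sample t power is 96.0% for one comparison. By simulation, all three gated tests succeed in 90.8% of trials. The stated power above 90% is reproduced. At 61 randomised, 61 × 0.95 ≈ 58 are evaluable.

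**Power for 50 mg versus placebo inside a level**, with n per arm in that level and a true effect of 1.5 everywhere, from the noncentral t with noncentrality 1.5/(2.1√(2/n)):

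| n per arm | power |
|---|---|
| 5 | 0.17 |
| 10 | 0.33 |
| 15 | 0.47 |
| 23 | 0.66 |
| 29 | 0.76 |
| 30 | 0.78 |
| 35 | 0.84 |
| 45 | 0.92 |

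**Chance that one level is significant and the other is not**, p₁(1 − p₂) + p₂(1 − p₁), because the two levels hold different patients:

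- 30/30: 2 × 0.776 × 0.224 = 0.35
- 29/29: 2 × 0.762 × 0.238 = 0.36
- 35/23: 0.838 × 0.341 + 0.659 × 0.162 = 0.39
- 45/15: 0.918 × 0.528 + 0.472 × 0.082 = 0.52

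The 35/23 split is 60% and 40% of 58 (34.8 and 23.2), which is prior exposure at its cap. The other splits are assumptions. 30/30 and 45/15 use 60 per arm as a round figure between 58 evaluable and 61 randomised.

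**Chance that the gate closes at 50 mg in at least one level**, 1 − p₁p₂: 1 − 0.762² = 0.42 at 29/29, and 1 − 0.838 × 0.659 = 0.45 at 35/23.

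**Comparison with an interaction test.** In 3,000 simulated trials with 58 per arm, a uniform 1.5-point effect and an even gender split, the gender interaction for 50 mg versus placebo was falsely significant in 4.8%. The within-level method gave discordant results for gender in 37%.

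**Power of the interaction test.** With 29 per cell, the SE of the difference between two effects is 2.1 × √(4/29) = 0.780. For an interaction of 1.5, 1.5/0.780 = 1.92, and power is Φ(1.92 − 1.96) ≈ 0.49.

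**Constant terms.** Within a prior-exposure level the exposure factor is constant; within baseline MMS 4 the covariate is constant. The six-column design (intercept, three treatment columns, exposure, baseline MMS) then has rank 5. Adding the treatment-versus-placebo contrast as a row leaves the rank at 5, so that contrast remains estimable.

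**The case against.** The best defence is that these analyses are exploratory. They sit under sensitivity analyses, SAP 7.5 admits low power, and no dose choice or claim in either document rests on a subgroup p-value. That stands, and it makes this an improvement rather than an error in the primary inference. But the caveat neither lifts the 5% sequence nor supplies a comparison between levels. The protocol's remark that p-values are descriptive closes its mixed-model paragraph in 9.2; the SAP does not carry it to subgroups, and SAP 6.5 sets 5% as the default.

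It can also be said that repeating the gate is inferred from one verb. That is fair: the SAP could mean the model alone. It should say which.

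A reader might infer four stronger things that the documents do not support:

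- *That some subgroup models cannot be fitted.* The constant term is only aliased with the intercept and the treatment contrasts survive. The practical difficulty with baseline MMS 4 is its size, which the documents do not give; SAP 5.2.4 allows that score only for patients enrolled on the original protocol.
- *That the gate removes the 100 mg and 25 mg estimates.* SAP 15.1.3 withholds comparisons with placebo, but it still presents least square means with confidence intervals.
- *That 18 country analyses will be run on about 244/18/4 = 3.4 patients per arm.* SAP 3.3 drops them and 15.1.4.2 does not list country. The list in 7.5 is a leftover.
- *That an interaction model costs nothing.* Its power is low, and across the seven two- or three-level factors simulated, under assumed subgroup shares, about 30% of trials with a uniform effect showed at least one false interaction.

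**Conclusion.** The point holds as a cheap improvement to the analysis and reporting of subgroups. The planned method cannot show whether the effect differs between levels. Under a uniform effect it gives a significant/non-significant split in roughly 35% to 52% of trials for a two-level factor, and in 39% for prior exposure at its cap. On the literal reading, it also withholds the comparisons of the other two doses with placebo in any level where 50 mg misses 5%.

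The figures assume the planning effect and SD, and a two-sample t-test in place of the ANCOVA. A prognostic baseline would raise power somewhat in every level. The split sizes are assumed apart from the 60% cap, which is itself an upper limit.

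A reader might conclude that the trial's type I error is inflated. It is not: the primary family of tests is untouched.

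**What to change.** Amend SAP 7.5 and 15.1.4.2 before database lock:

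- For each baseline factor with two or more levels, fit one ANCOVA on the whole FAS with a treatment-by-subgroup term. Report each dose's difference from placebo with a 95% CI per level in a forest plot, plus a descriptive interaction p-value. Apply no gate and no 5% declaration within levels.
- Treat corticosteroids, immunosuppressants and 5ASA as three separate yes/no factors, because a patient can take more than one.
- Leave the Week 16 ABX464-NGlu AUC subgroup, which SAP 3.3 keeps if data are available, out of the interaction model. Placebo patients have no AUC. Show it as estimates versus placebo only.
- Give only descriptive statistics for baseline MMS 4 if it is too small to model, or pool it with 5 to 6. State the choice in advance.
- Say how interactions are handled if the rank ANCOVA of 15.1.3 is triggered, because an effect that is uniform on the MMS scale need not be uniform on ranks.
- If within-level models are kept, state that the term constant in that level is dropped.
- Reconcile the country list in 7.5 with 3.3.

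The cost is SAP wording and one model per factor, with no new data. The drawback is the low power of the interaction tests and their number, so the p-values should be read alongside the estimates and intervals and not as pass or fail.
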